- 7) interviewers administer the appropriate research documentation forms (see Assessment – Research Documentation Forms section)
- 8) interviewers look for reporting inconsistencies and socially desirable responses; and
- 9) consistency checks on reporting are built in as part of the interview process.

The Project Director will periodically sit in on interviews to ensure compliance with interview protocols and to identify problems that need correction. As a quality check, the Project Director will randomly call 10% of participants for whom interview forms are on file to verify that the interview took place and to ask about suggestions on interview procedures (see ISAP's data integrity policy in Appendix C).

RANDOMIZATION

In the Admission Phase, clients will be randomized to the Admission Incentive group or to the Admission Information group. Thus, each client has a 50/50 chance of gaining entry to the Incentive group or the Information group. Those clients in the Admission Phase who show up at Walden House and complete intake process will be consented and re-randomized to the Attendance Incentive group or to the Attendance Information group. In both cases, clients will

be randomly assigned to one of the study conditions using the Urn Randomization Program (version 1.10, developed at Yale University for Clinical Trials Network studies). Urn randomization is a procedure to maintain balance and minimization of bias across study groups for selected characteristics expected to be related to outcome (Stout, Wirtz, Carbonari, & Del Boca, 1994). The following baseline variables that are strongly associated with drug use and/or crime outcomes will be used in urn randomization:

- Race/ethnicity (African American vs. White/Hispanic/Other)
- Risk for recidivism (using the score on the Lifestyle Criminality Screening Form: 0-7 vs. 8-20)
- Parole status (In-Custody Drug Treatment Program vs. voluntary SAP graduate) – because custody arrangements differ between the two groups. In-Custody Drug Treatment Program (ICDTP) clients are considered to be in-custody and cannot leave the program premises without a staff member, while voluntary SAP graduates are not required to stay in the program.

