Client Evaluation of Self at Intake (CESI): Motivation Scales. This TCU form (Simpson & Joe, 1993) includes short scales for treatment motivation, psychological functioning, social functioning, and criminal thinking completed by the client. This study will use the motivation scales, but will modify the readiness for treatment subscale to refer specifically to aftercare. The motivation scales correspond to the Stages of Change model as delineated by Prochaska and DiClemente (1986). The self-assessment of drug use ($\alpha=.91$) scale consists of nine items that are intended to differentiate between those who have begun the contemplation stage and those who remain in the precontemplation stage. The desire for help ($\alpha=.83$) scale consists of seven items assessing the transition from general acknowledgment of a drug problem to recognition of the need for help. Finally, the readiness for treatment ($\alpha=.63$) scale has eight items intended to assess willingness to enter and comply with treatment, and represents the completion of the above transition and the beginning of the action stage.

Counseling Utilization Form. Once a week, the research assistant will check each participant's clinical records and note how many treatment sessions (individual or group) were scheduled for the participant and how many the participant attended.

CM Record Form. In order to check on protocol adherence and to collect data for analysis, this form provides a record of information about attendance, date of the receipt of the voucher, amount of the voucher, and items redeemed.

Treatment Termination Form. This short form records whether a participant completed the intervention and, if relevant, the reason for early termination (e.g., incarceration, transfer to another program, voluntary withdrawal from study and reasons for doing so). (Note that except for participants who request to be removed from the study, all randomized subjects will be tracked for follow-up.)

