In examining study design issues, we will investigate possible bias arising from the recruitment process by examining, for the Admission Phase and the Attendance Phase, reasons for ineligibility, reasons for refusal, and characteristics of clients who are ineligible or who refuse to participate. In addition, we will determine treatment status at the end of the intervention and reasons for early withdrawal from treatment. Focus group information and responses on the Client Satisfaction Questionnaire will be used to assess whether the findings might be biased because of resentful demoralization.

A baseline equivalency analysis for the Admission Phase and for the Attendance Phase will determine whether randomization has resulted in balance between study groups on baseline variables that may affect outcomes (e.g., age, race/ethnicity, primary drug problem, motivation). First, bivariate tests of group differences will be conducted on selected baseline variables, including those measures that have been shown in previous studies to covary with study outcomes. Second, variables (if any) that significantly differ between groups will be entered into a logistic regression model in which the dichotomous outcome variable is group membership. Measures that are significant predictors of group membership in this model will be used as covariates in subsequent outcome analyses. Although failure to find differences at baseline will not guarantee that the groups are equivalent, since they could still differ on unmeasured characteristics, it does rule out differences on those characteristics that are assessed.

Because of possible analysis problems caused by missing data, the main strategy to reduce missing data will be to train and monitor interviewers to ensure that data are collected at the designated assessment points from all participants and that that interviews are reviewed for skipped questions. ISAP's Data Management Center will regularly provide reports to research staff of the amount and pattern of missing or incorrect data so that data problems can be

resolved early. In analyses, missing data will be explored through frequency distributions. Missing data will be addressed using maximum likelihood (ML) or multiple imputation (MI) estimates from incomplete data (Little & Rubin, 1987; Shafer & Graham, 2002). Alternatively, statistical techniques that allow for missing data may be used (e.g., generalized linear models).

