Hypothesis tests are based on the assumption of group equivalence due to random assignment. However, if preliminary analysis indicates significant baseline differences, then additional control variables will be included in the analyses. Hypotheses will be tested using a two-sided .05 level of significance.

Hypotheses will initially be tested using t-tests and chi-square tests. T-tests will be used to conduct pairwise comparisons of participants in the study groups on outcomes measured as a single continuous variable. For categorical and binary outcome variables, we will use chi-square analysis. If covariates are required, analyses will be extended to ordinary least squares (OLS) or logistic regression as appropriate to the scale properties of the dependent variable. Because of missing data, inclusion of covariates, and/or repeated measures for binary outcomes, analyses may be extended to generalized linear models (McCullagh & Nelder, 1989). Structural equation modeling will be used to determine whether the effect of incentives on distal outcomes is mediated by program admission, treatment activities, admission, or retention (Kaplan, 2000).

For each hypothesis, an effect size will be calculated. The index of effect size will be the standardized mean difference (calculated as the difference between two groups divided by the pooled standard deviation); for proportions, the equivalent effect size is calculated using the arc sine transformation (Lipsey & Wilson, 2001). An effect size for study outcomes will provide a

quantitative indication of the magnitude of the difference between groups; it will also be useful in calculating power for any future study of this intervention.

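### The only stated covariate rule, imbalance between arms, cannot protect the planned mediation model from confounding of the mediator-to-outcome path

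*Protocol*

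**What the plan says.** All places are in the protocol.

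- **The mediation analysis.** Hypothesis Testing states: "Structural equation modeling will be used to determine whether the effect of incentives on distal outcomes is mediated by program admission", with treatment activities and retention as the other candidate mediators. It names no covariates for that model.
- **The covariate rule.** Design Analyses sets a two-step screen. First, "variables (if any) that significantly differ between groups will be entered into a logistic regression model" with study group as the dependent variable. Second, "Measures that are significant predictors of group membership in this model will be used as covariates in subsequent outcome analyses". Hypothesis Testing repeats the principle: "Hypothesis tests are based on the assumption of group equivalence due to random assignment", but "if preliminary analysis indicates significant baseline differences, then additional control variables will be included in the analyses". Neither section selects a variable because it predicts retention or the outcome.
- **Variables tied to both.** Randomization lists race/ethnicity, recidivism risk (LCSF score) and parole status as urn factors, chosen for their strong association with drug use or crime outcomes. On parole status it says that in-custody "clients are considered to be in-custody and cannot leave the program premises without a staff member", whereas voluntary graduates need not stay. Under Data Sources, the readiness scale of the CESI is described as "intended to assess willingness to enter and comply with treatment".

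**The concern.** Assignment to incentives is randomized; retention and treatment activities are not. Balance between arms protects the effect of arm on retention and the effect of arm on outcome. It does nothing for the path from retention to outcome. A variable equally distributed in the two arms can still determine who stays and who relapses or is rearrested, and if it is left out, its influence is credited to retention.

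A screen on between-arm differences cannot find such a variable. It is least likely to find the urn factors, because the allocation procedure is built to balance them. Parole status is the awkward case: the protocol itself links it to leaving the program and to outcome, and then balances it in the Attendance Phase.

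At stake is the trial's reading of mechanism. The introduction argues that greater treatment exposure improves long-term outcomes, and the mediation model speaks to that link.

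**Working it through.** The protocol gives no figure for this model, so there is none to reproduce. The check asks how often mediation would be declared when there is none.

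**Inputs from the protocol.** About 170 participants in the follow-up interview sample (Power Analysis), 1:1 allocation (Randomization), two-sided 0.05 (Hypothesis Testing), and d = 0.34 for incentives on attendance (the attendance study cited in Power Analysis).

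**Assumptions.** One baseline confounder, independent of arm, has the same correlation r with retention and with outcome. The documents give no such correlation, so r is varied. Retention and arm have no true effect on outcome. Linear path models stand in for the structural equation model. Mediation is declared when both the arm-to-retention and the retention-to-outcome paths are significant.

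**Closed form.**

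1. With the confounder omitted, the spurious retention-to-outcome path is b = r × r.
2. Its standard error is about 1/√170 = 0.0767.
3. Rejection rate: p = Φ(b/0.0767 − 1.96) + Φ(−b/0.0767 − 1.96).
4. Under the imbalance screen a randomized variable enters in about 5% of trials, and the path is then tested correctly. The rate becomes 0.95p + 0.05 × 0.05.
5. Power for the arm-to-retention path: 0.34 × √(85/2) = 2.217, and Φ(2.217 − 1.96) = 0.60.
6. False mediation is about 0.60 times the result of step 4. With the confounder always included it is about 0.60 × 0.05 = 0.03.

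**Results**, beside a simulation of 4000 trials per setting with the screen applied literally:

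| r | b | p (step 3) | step 4 | false mediation, closed form | simulated, imbalance rule | simulated, always adjusted |
|---|---|---|---|---|---|---|
| 0.1 | 0.01 | 0.052 | 0.052 | 0.031 | 0.028 | 0.029 |
| 0.2 | 0.04 | 0.082 | 0.080 | 0.048 | 0.046 | 0.030 |
| 0.3 | 0.09 | 0.217 | 0.209 | 0.125 | 0.127 | 0.036 |
| 0.4 | 0.16 | 0.550 | 0.525 | 0.315 | 0.317 | 0.039 |
| 0.5 | 0.25 | 0.903 | 0.860 | 0.516 | 0.519 | 0.041 |

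A second set of simulations gave 5%, 12% and 31% at r = 0.2, 0.3 and 0.4.

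**Variations.**

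- With d = 0.50 on retention, false mediation is 8%, 18%, 48% and 80% at r = 0.2 to 0.5, against 4–5% with adjustment.
- With 200 participants (records outcomes, no attrition) and d = 0.34, it is 16% at r = 0.3 and 39% at r = 0.4, against 3% and 4%.
- With correlations of 0.3 and −0.3 the mean spurious path is −0.087, and mediation is declared in 13% of trials in the wrong direction. Confounding of that sign would roughly cancel a true path of +0.09, so it can also hide real mediation.

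**The case against.** The strongest reply is that the protocol never says the mediation model takes covariates only when they differ between arms. The sentence on that model is silent, mediation is not among H1–H9, and the specification of one secondary model normally belongs in a statistical analysis plan, which is not at hand. The first part stands: applying the rule is an inference. It is a strong one, because the rule covers the analyses of the same section and later outcome analyses, and the protocol states no other. Power Analysis mentions covariates for power, and Other Analyses plans to study motivation and predictors of participation, but neither says what enters the mediation model. The point is therefore about a stated rule unsuited to this model, not about missing detail.

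Three stronger readings are tempting and not supported.

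- **That the planned model will make retention look like a mediator.** It can. The size rests on correlations the documents do not give, and at r = 0.2 or below there is almost no inflation of false mediation. That motivated men stay longer is plausible, but the protocol gives no figure for it.
- **That the trial's main conclusions are at risk.** The intent-to-treat comparisons for H1–H9 rest on randomization and are untouched.
- **That this model is the plan's only evidence for its rationale.** Long-term benefit is tested by randomized comparisons in H5–H9, and a complier average causal effect analysis is proposed if compliance is a problem.

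**Conclusion.** The point holds as a weakness of a secondary analysis that should be corrected. If the imbalance rule governs the mediation model, balanced confounders of mediator and outcome will nearly always be left out, and the protocol itself identifies one in parole status. The error is negligible for weak confounders. At correlations of 0.3 to 0.4 with both retention and outcome, false mediation is roughly three to eight times the rate with adjustment (0.127/0.036 = 3.5; 0.317/0.039 = 8.1). These figures assume a single confounder, linear models and a continuous outcome. Several confounders could add up or offset one another. The direction of the bias cannot be fixed from the documents.

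**What to change.** In Hypothesis Testing, state that the mediation model adjusts both mediator and outcome for a prespecified set of baseline variables, whatever their balance between arms:

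- the urn factors of the phase analysed: race/ethnicity and LCSF risk in both phases, and parole status in the Attendance Phase only (Randomization says all Admission Phase subjects are voluntary graduates, so it does not vary there);
- where a baseline interview exists, CESI motivation and readiness, TCU drug severity, BSI, antisocial personality disorder and BIS-11 impulsiveness.

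Add a sensitivity analysis showing how large a residual mediator–outcome correlation would remove the indirect effect, and describe that effect as conditional on no unmeasured confounding.

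The cost is a few degrees of freedom at about 170 participants, plus handling of missing covariates. The second item needs care: Recruitment – Intake Procedures says the Attendance Phase has no baseline interview, while Baseline Interview Procedures allows interviews at Walden House. Whether men who enter the Attendance Phase directly supply these measures should be settled, and the treatment of those without them stated in advance.

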APPENDIX B - Voucher Incentive Quiz

(the following is adapted from the HAART Training Manual, pp.775-776)

1. I will earn vouchers for _____
 - a) attending research interviews.
 - b) providing drug-free urine samples each week.
 - c) attending treatment each day.

2. How do I earn the maximum number of vouchers?
 - a) Attending my treatment as scheduled.
 - b) Staying in treatment.
 - c) Being in treatment continuously for 22 weeks.
 - d) All of the above.

3. At the first week, I will receive _____ in vouchers per day, if I attend treatment “on schedule.”
 - a) \$0.50
 - b) \$2.50
 - c) \$3.60
 - d) \$12.50

4. If I go AWOL from the treatment program and return to treatment what happens?
 - a) The amount I already earned will still be there.
 - b) I will lose all my money and have to start over again.

5. On each day of Week 2, my vouchers will be worth _____ more than they were worth during Week 1, if I continue to attend treatment sessions “on schedule” each day.
 - a) \$0.33
 - b) \$0.50
 - c) \$1.00
 - d) \$6.00

6. If I miss a single treatment day at the scheduled time, the voucher value will be reset to _____ per day.
 - a) \$0
 - b) The value I earned the day before I missed a treatment day.
 - c) The value I earned two weeks ago.
 - d) The initial low value of \$2.50 per day

7. What happens if I am sick or can't attend treatment session for personal reasons?
 - a) I will have to reschedule the treatment session.
 - b) It doesn't matter if I miss one session, as long as I don't miss a whole week.
 - c) If I don't have a legitimate excuse, including WH staff approval or a verifiable doctor's note, I will receive no voucher credits until the Monday after I return to treatment. Also, my voucher value will be reset to \$2.50 per day for two weeks of continuous attendance, and then on the third week my voucher value will go back to what it was before I missed a treatment day.

- d) If there is a legitimate excuse, with prior WH staff approval or a verifiable doctor's note, the rate of voucher earnings will continue for hospital stays of 1-3 days, or for longer absences will simply be paused and I will resume my earning levels when I return.
- e) Both c and d.

BIBLIOGRAPHY

- Alessi, S. M., Hanson, T., Wieners, M., & Petry, N. M. (2007). Low-cost contingency management in community clinics: delivering incentives partially in group therapy. *Experimental and clinical psychopharmacology*, *15*(3), 293-300.
